3. STUDY DESIGN

To determine the effect of the PR methodology, a pragmatic open-label multicenter cluster randomized controlled trial (cRCT) will be conducted in nursing teams working in primary care, from January 2024 to March 2026 in Utrecht, the Netherlands. We define a cluster as one nursing team in primary care, which is a group of registered nurses (RNs) and nurse assistants (NAs) collaborating within one home care organization and within the same district with support of specialized nurses (SN) and/or nurse practitioners (NPs). The trial consists of an intervention group and a control group. To enhance heterogeneity of usual care in the control groups and limit the risk of bias, randomization of the intervention will be conducted within one primary healthcare organization.

The intervention starts with the adequate identification of patients in need of palliative care by means of the surprise question “would I be surprised if this patient dies in the next year?”. If the answer to the question is “no”, the patient is suitable for receiving palliative care. After identification the PR methodology is followed by four phases. step 1: map out the individual situation, symptom burden and quality of life of the patient, step 2: summarize the current problems and develop a proactive policy plan, Step 3: evaluate the effect of the proactive policy plan on the symptom burden and quality of life of the patient, step 4: adjust the policy plan if necessary and continue evaluating. The Utrecht Symptom Diary – four dimensional (USD-4D) will be used to monitor the individual situation, symptom burden and quality of life of patients, as described in step 1. This is a Patient Reported Outcome Measure (PROM) and is validated in palliative care populations.

The nursing teams selected as control group will continue to provide usual care to patients with a life-limiting illness. We define usual care as “care that patients with a life-limiting illness, living at home, would be expected to receive as part of normal practice from that specific homecare organization”(29). To gain insight into normal practice of the control group, we will consult the organization’s current safety standards, guidelines, and protocols. Additionally, questions regarding normal practice will be asked during interviews with healthcare professionals.

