4. STUDY POPULATION

4.1 Population (base)

The study population consists of patients with a life-limiting illness, receiving palliative care from nursing teams that work at two large homecare organizations in Utrecht, the Netherlands. Patients of different sex and age categories will participate in this study. All patients live at home, in the region of Utrecht and suffer from a wide range of life-limiting illnesses. Family caregivers participating in this study are the primary caregiver of the patient and may live in other regions of the Netherlands than the patient, since they are not bound by the range of a homecare organization.

Nursing teams usually consist of nurse assistants (NAs), registered nurses (RNs), specialized nurses (SNs) and nurse practitioners (NPs). All types of nurses have different educational backgrounds and therefore different job descriptions and responsibilities. NAs have three years of practical educational training after receiving their diploma. RN can be educated at an intermediate or a higher level. An intermediate RN receives at least 6400 hours of practical and theoretical education and RN with a higher level of education receives at least 6720 hours of education, of which a minimum of 1535 hours of theoretical courses and 2300 hours of on-the-job instruction. Both educational programmes take 4 years to complete, however, only the higher level of nursing education results in Bachelor of Nursing degree. Additionally, both RN can specialize in a certain health field, for example to become a district nurse (DN) or oncology nurse, which are SNs. RN with a higher level of nursing education can become NPs by completing a Master's of Advanced Nursing Practice, which comprises of 2 additional years of practical and theoretical education(30,31).

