4.4 Sample size calculation

As concluded by Adams et al., there is always a certain degree of uncertainty in estimating the magnitude of the intraclass correlation coefficient (ICC) for cRCTs beforehand(32). Therefore, the following calculation aims to provide the most accurate estimate of the required sample size, in order to demonstrate an effect. Based on our experience required during KWASA, a pilot study, primary nursing teams identify on average twenty patients with a life expectancy of one year or less. Hence, we expect the inclusion of twenty patients per nursing team to be feasible during this study. To estimate the number of clusters as accurate as possible, we considered different ICCs and different effect sizes for the intervention group(I). We calculated the number of clusters necessary assuming a power of 80%, an alpha of 5%, an effect size of 30% in the control group (C) and an effect size of 40% and 60% in the intervention group. Table 1 shows an overview of the results of our calculations.

Table 1. Overview results sample size calculation with different ICC and effect size.

ICC	N patients	I	C	N clusters
0.02	20	0.4	0.3	26
0.01	20	0.4	0.3	23
0.005	20	0.4	0.3	21
0.001	20	0.4	0.3	20
0.02	20	0.6	0.3	5
0.01	20	0.6	0.3	4
0.005	20	0.6	0.3	4
0.001	20	0.6	0.3	4

* ICC = Intraclass correlation coefficient. N patients = Number of patients in the cluster.
I = Intervention group. C = Control group. N cluster = Number of clusters.

According to our calculation a total of 20 clusters in each arm is the best fit for this study, assuming an effect size of 40% and an ICC of 0.001. A higher ICC results in a limited number of extra clusters, therefore, a total of 800 patients divided into 40 clusters is in our opinion the most appropriate. All calculations have been conducted with help of a methodologist from the Julius Centre and by means of the ClusterPower package of RStudio (Vienna, Austria), version 2022.12.0+353.

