Lastly, an assessment of demographic characteristics and perceived care burden on the primary caregiver is performed by the research team. Thereafter, at one-, three- and six-months perceived care burden is evaluated by telephone using the EDIZ rating scale. After each assessment the primary caregiver will be offered support of a NP, specialised in PC to talk about possible thoughts or concerns raised by completing the questionnaires.

Blinding:

In causal studies, blinding is performed ideally at participant, data collection and data analysis level. In this case, however, blinding at the analysis level is the only feasible.

- The participants are not blinded. Patients, primary caregivers, and the nursing teams will all be aware of their allocation to the intervention group, since the method Palliative Reasoning will be implemented in daily care.
- The data collection will not be performed blindly. Firstly, the data are collected by local nurses who are aware of their allocation. Secondly, the research team who is involved in training the participants are also aware of the allocation, which is necessary to ensure an in-depth exploration of the experiences of the nursing team

during the up-following qualitative part of this study. This part will be described in a different research protocol, which is part of phase 4 of this study.

- Data analysis will be performed blinded. The researcher performing the data analysis will be blinded for the group allocation using labels. The labels will be opened after the analysis.

Randomization and allocation:

The clusters will be randomized through a simple randomization method with the Clinical Trial Randomization Tool from the National Cancer Institute(40,41). To minimize the risk of allocation bias, we will stratify between both homecare organization. The teams are informed about their allocation by the research team.

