6. STATISTICAL ANALYSIS

6.1. Primary study parameter(s)

To determine the effect of the SMEtH-intervention on the perceived symptom control after 1 month of patients of each nursing team, a mixed effects logistic regression analysis will be conducted. We will control for the following baseline measurements: age, gender, primary diagnosis, and performance status. Missing data are imputed using multiple imputation (MICE package in R) or if necessary, Bayesian imputation and analysis (Joint AI package in R). The quantitative data will be presented as odds ratio and 95% confidence interval (CI) in tables and graphs for the visualization of the results. Additionally, all analyses of primary and secondary study parameters are conducted by means of the statistical program RStudio, version 2022.12.0+353. (Vienna, Austria), and are considered statistically significant if $\alpha \leq 0.05$.

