Plan Overview

A Data Management Plan created using DMPonline

Title: Symptom Management Essentials at Home (SMEtH)-study

Creator: [name]

Principal Investigator: [name] [name]

Contributor: [name], [name]

Affiliation: UMC Utrecht

Funder: ZonMw (Nederlands)

Template: UMC Utrecht DMP with DPIA

Project abstract:

Rationale: Despite the current national quality guidelines, symptom management in patients and family caregivers with a life-limiting illness, receiving domiciliary palliative care in the Netherlands, is still suboptimal. Barriers that have been identified are the identification of patients with PC needs, the collaboration with GPs and other caregivers, knowledge on quality of pc at home and optimizing autonomy, communication, and competences. To support nursing teams in the provision of palliative care, the method Palliative Reasoning has been developed, which is a systematic symptom management approach.

Objective: The aim is to determine the effect of the Palliative Reasoning methodology on perceived symptoms of patients and family caregivers dealing with a life-limiting illness and receiving palliative care at home by implementing this methodology in homecare nursing teams.

Design: Pragmatic open-label multicenter cluster randomized controlled trial.

Population: Patients (≥ 18 years) dealing with a life-limiting illness and with a life expectancy of less than one year, receiving palliative care by nursing teams working in homecare organizations and their family caregiver.

Primary study parameter: perceived symptom control of patients and family caregivers dealing with a life-limiting illness, after one month of implementing the SMEtH-intervention, measured with a one item question "Do you feel your symptoms are under control? Yes/No?".

Statistical analysis: Mixed effects logistic regression analysis, controlled for age, gender, primary diagnosis, and performance status.

ID: 131142

Start date: 01-04-2022

End date: 31-03-2026

Last modified: 04-08-2023

Grant number / URL: 80-86300-98-060

Symptom Management Essentials at Home (SMEtH)-study

1. General features

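### Section 5.2 calls the allocation of teams both simple and stratified by homecare organisation, with no stated restriction, and the primary model leaves organisation out.

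*Protocol*

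**What the plan says.** Protocol section 5.2, under randomisation and allocation, makes two consecutive statements: "The clusters will be randomized through a simple randomization method with the Clinical Trial Randomization Tool from the National Cancer Institute", and "To minimize the risk of allocation bias, we will stratify between both homecare organization". Neither document gives a block size, an allocation ratio within organisation, minimisation or any other restriction.

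Three other places in the protocol bear on what is meant:

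- Section 4.4 takes the lowest ICC in Table 1, which is 0.001, and concludes that "a total of 20 clusters in each arm is the best fit for this study, assuming an effect size of 40% and an ICC of" that value.
- Section 3 says that "randomization of the intervention will be conducted within one primary healthcare organization".
- Section 4.1 recruits from "nursing teams that work at two large homecare organizations in Utrecht".

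The primary analysis is a mixed effects logistic regression. Section 6.1 gives its adjustment as: "We will control for the following baseline measurements: age, gender, primary diagnosis, and performance status". The project abstract in the document supplied as the SAP gives the same list: "Mixed effects logistic regression analysis, controlled for age, gender, primary diagnosis, and performance status". Organisation is in neither list. Section 6.2 adds death for the secondary outcomes, but not organisation.

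**The concern.** The allocation text can be read in two ways.

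1. **Literal.** Each team is assigned independently with probability one half. Doing this separately in each organisation gives the same distribution of allocations as doing it once for all teams. The stratification then has no effect, and neither balance by organisation nor 20 teams per arm is secured.
2. **Restricted.** A fixed number of teams per arm is drawn within each organisation. Section 4.4 fits this, and so does section 3 if it means within each organisation. The word simple is then wrong.

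Whoever prepares the allocation list cannot tell from the text which procedure to run.

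The analysis has a gap on either reading. Under reading 1, chance differences in organisation mix add noise that the model does not remove. Under reading 2, the design removes the organisation difference from the treatment comparison, but a model without organisation still counts it as variation between teams. The standard error is then too large and power is lost. Both costs arise only if symptom control differs by organisation. The documents report no such difference, but section 3 defines usual care as the care a patient "would be expected to receive as part of normal practice from that specific homecare organization", so a difference is plausible.

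**Working it through.** **Inputs from section 4.4:** 40 teams, 20 patients per team, 40% against 30%, alpha 5% (taken as two-sided), Table 1 ICCs from 0.001 to 0.02. **Assumed, because not given:** teams per organisation (20+20 to 10+30), and the share *s* of between-team variance that is due to organisation (all, half, none).

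**The plan's own figure.** Teams per arm = (sum of quantiles)² × 2 × 0.35 × 0.65 × (1 + 19 × ICC) / (20 × 0.10²). At ICC 0.001 with normal quantiles: 7.849 × 0.455 × 1.019 / 0.20 = 18.2. With t quantiles it is 19.2, rounded up to 20. The t version reproduces all eight rows of Table 1, so the sample size calculation is not in question here.

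**Reading 1: chance imbalance.** With independent assignment, the number of teams in one arm is Binomial(40, 0.5).

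- Exactly 20:20 has probability 0.125; 16:24 or worse has probability 0.268.
- Unequal numbers alone matter little. At ICC 0.001 the normal formula gives power 0.837 at 20:20 and about 0.82 at 16:24.
- Enumerating both organisations, the arms differ in organisation mix by 20 points or more in 26.8% (20+20), 20.9% (15+25) or 17.4% (10+30) of allocations.

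**How far such an imbalance can move the estimate.** If organisation explains all between-team variance and the stated ICC holds, the gap between organisations is √(ICC × 0.30 × 0.70 / (w(1 − w))), with w the share of teams in one organisation. The shift from a 20-point mix difference is 0.20 × gap. The standard error is √((1 + 19 × ICC) × (0.24 + 0.21) / 400).

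| ICC | Gap, w = 0.5 and 0.25 (points) | Shift (points) | Standard error (points) |
|---|---|---|---|
| 0.001 | 2.9 and 3.3 | 0.6 and 0.7 | 3.4 |
| 0.02 | 13.0 and 15.0 | 2.6 and 3.0 | 3.9 |

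The planned difference is 10 points. These gaps depend on the ICC: a 20-point gap would need an ICC of 0.036 to 0.048, above anything in Table 1.

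**Reading 2: size of the excess standard error.** The variance of a team proportion is proportional to 1 + 19 × ICC. Removing organisation takes off 20 × s × ICC. The ratio of the reported to the true standard error is therefore √[(1 + 19 × ICC) / (1 + 19 × ICC − 20 × s × ICC)]:

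- ICC 0.02, s = 1: √(1.38 / 0.98) = 1.19.
- ICC 0.02, s = 0.5: √(1.38 / 1.18) = 1.08.
- ICC 0.001, s = 1: √(1.019 / 0.999) = 1.01.

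**Simulation.** 40,000 runs per cell, with team proportions regressed on arm with or without organisation. This stands in for the mixed logistic model and has no patient covariates. Power at ICC 0.02 with 20+20 teams, without and with the term:

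| Share due to organisation | Simple | Restricted |
|---|---|---|
| All | 68.6% / 81.1% | 72.7% / 83.3% |
| Half | 69.0% / 74.2% | 71.1% / 76.2% |
| None | 69.4% / 68.3% | 70.3% / 70.2% |

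Results for 10+30 teams are within 1 point of these.

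- Restricted, term omitted, share all: mean model standard error 3.93 against a true 3.32 (ratio 1.18, in line with the formula), coverage 97.8%, type I error 1.9%. Share half: 3.92 against 3.62, coverage 96.5%, type I error 3.2% to 3.3%.
- Simple, term omitted: mean estimate 9.96 to 10.03, type I error 4.7% to 5.2%. There is no bias on average and no excess of false positives.
- ICC 0.01, restricted, share all: 77.6% / 82.9%.
- ICC 0.001, share all: simple 81.0% / 80.6%, restricted 81.8% / 82.3%.

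**The case against.** The strongest reply has four parts.

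- **The covariate list may not be the full model.** Section 6.1 lists patient characteristics and does not spell out the team random effect either. The document supplied as the SAP is a data management plan, and its sections on analysis and archiving refer to a separate analysis plan that is not available here. This stands as a limit: the claim is that organisation is missing from the model as stated in these documents. But both documents give the same four covariates and neither hints at more.
- **The allocation point may be loose wording for stratified randomisation.** That is quite possible. The text still has to say so, because the list cannot be generated from it, and on that reading the omission of organisation is what costs power.
- **The larger figures need the highest ICC in Table 1 and a large organisation share.** This is fair. In a random-intercept logistic simulation (2,000 runs per cell, 20+20 teams, ICC 0.02, restricted), power without and with the term was 73% and 82% if organisation explains all between-team variance, 71% and 76% if half, and 70.5% and 73% if one fifth. A modest share therefore costs about 2 points. Type I error with the term omitted and share all was 2.8%, so the linear stand-in overstates the conservatism somewhat. Diagnosis and performance status, which the plan adjusts for, could also absorb part of a difference due to case mix.
- **At the design ICC of 0.001 almost nothing changes.** This is also true, but section 4.4 itself treats the ICC as uncertain and tabulates values up to 0.02.

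**Conclusion.** The concern holds. Section 5.2 does not define one allocation procedure, and the stated primary model omits the only stratification factor in both documents.

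The consequence is a conditional loss of precision. The effect estimate is not biased on average, and false positives do not exceed the nominal rate. With restricted allocation and ICC 0.02, omitting organisation costs about 11 points of power if organisation explains all between-team variance (83.3 − 72.7 = 10.6), about 5 points if it explains half, about 2 if one fifth, and none if the organisations do not differ. At ICC 0.001 it costs about 1 point or less.

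These figures rest on the assumed team split and organisation share, and mostly on a team-level stand-in for the logistic model; the logistic simulation agrees on direction and size of the power loss. The reading of the text is certain. The size of the loss is not, because the documents do not say how far the two organisations differ. The change should be made because it costs next to nothing and the allocation text needs clarifying in any case.

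**What to change.** - **Section 5.2:** replace the simple method with restricted 1:1 allocation of teams within each homecare organisation. Use concealed permuted blocks or, if all teams are known at the start, a random half of the listed teams in each organisation. Reword section 3 so that it clearly means within each of the two organisations.
- **Section 6.1 and the statistical analysis line of the SAP abstract:** add homecare organisation as a fixed effect in the primary model. Two levels are too few for a random effect. The same term belongs in the secondary models of section 6.2.

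The two changes belong together. Under simple allocation the term costs about 1 point of power if the organisations do not differ (69.4% against 68.3%); under restricted allocation it costs nothing measurable (70.3% against 70.2%).

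The cost is a sentence or two of text, one covariate and a different randomisation list. No patients, visits or staff are added. The allocation rule must be settled before teams are randomised, and the covariate before the data are analysed.

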5.3. Withdrawal of individual subjects

Patients and caregivers will be informed that consent may be withdrawn at any stage of the study, without stating a reason or any consequences.

5.4. Replacement of individual subjects after withdrawal

After the withdrawal of a patient, the patient will specifically be asked if the collected data up to that point may be used for the purposes of this study. If not, data regarding this patient will be removed from the database.

6. STATISTICAL ANALYSIS

6.1. Primary study parameter(s)

To determine the effect of the SMEtH-intervention on the perceived symptom control after 1 month of patients of each nursing team, a mixed effects logistic regression analysis will be conducted. We will control for the following baseline measurements: age, gender, primary diagnosis, and performance status. Missing data are imputed using multiple imputation (MICE package in R) or if necessary, Bayesian imputation and analysis (Joint AI package in R). The quantitative data will be presented as odds ratio and 95% confidence interval (CI) in tables and graphs for the visualization of the results. Additionally, all analyses of primary and secondary study parameters are conducted by means of the statistical program RStudio, version 2022.12.0+353. (Vienna, Austria), and are considered statistically significant if $\alpha \leq 0.05$.

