5. METHODS

5.1 Study parameters/endpoints

5.1.1. Main study parameter/endpoint

The main study parameter is “perceived symptom control of patients and family caregivers dealing with a life-limiting illness, after one month of implementing the SMEtH-intervention”. Perceived symptom control is defined as the perception of symptom control by a patient, assessed at enrolment and after one month by a one item question: “Do you feel your symptoms are under control? Yes/ No?”. The endpoint of one month has been chosen to limit the number of missing data due to death of participating patients.

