5.2. Study procedures

Firstly, this study will start with the assessment of team characteristics, to develop a suited implementation strategy that fits the team and local context but does not influence the fidelity of function. Depending on the composition of the team, education levels and competences in the team, education and training content will be established by a team of coaching experts,

consisting of independent NPs and GPs with extensive experience in PC and PR. The intervention group will be educated in identifying patients with PC needs and will be taught how to apply PR in a four-day training with practical assignments. After two weeks of providing this four-day training to the nursing team, team coaches will be coached by means of a coaching on the job trajectory once a fortnight by the team of expert coaches. Team coaches that will be trained work as NP or SN within one of the organizations and are teamed up with RNs of the general nursing team. The team coaches will perform day to day coaching on the job. The implementation of the intervention will take approximately one month and will be planned in collaboration with the teams and the coaches.

Additionally, nurses who are enrolled in the study will be invited to complete questionnaires individually at enrolment and at six months about their own current symptom management practices, roles and responsibilities, collaboration, communication, and competences.

Secondly, the research team will perform an assessment of baseline measurements in participating patients and request to complete a questionnaire regarding demographic characteristics. The assessment of baseline measurements will be performed by post, mail, telephone, or teleconsulting depending on what is the most suitable and least burdensome for the patient. Subsequently, patients will complete at one-, three- and six-months a questionnaire containing questions regarding symptom control, quality of life and symptom burden. If these questionnaire reveals that a patient does not suffer from any symptoms, it will be excluded from the study. However, the excluded patients will be asked to complete the Lastmeter questionnaire to detect symptoms that may develop at a later stage, to be able to reconsider their inclusion in the study. After each questionnaire and/or assessment patients will be offered support of a NP, specialised in PC to talk about possible thoughts or concerns raised by completing the questionnaires.

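### The primary model omits homecare organisation, the randomisation stratum, and the enrolment answer to the primary question, whose timing relative to the intervention is not fixed

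*Protocol*

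**What the plan says.** Protocol section 6.1 specifies a mixed-effects logistic regression of symptom control at one month and lists the adjustment set: "We will control for the following baseline measurements: age, gender, primary diagnosis, and performance status". The Plan Overview of the document filed as the SAP (a data management plan) repeats it: "Mixed effects logistic regression analysis, controlled for age, gender, primary diagnosis, and performance status".

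Two other variables are on hand at baseline:

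- **Homecare organisation.** Section 5.2, under randomisation, says "we will stratify between both homecare organization". The same paragraph says "The clusters will be randomized through a simple randomization method" and gives no rule for balancing arms within organisation. Section 3 adds that "randomization of the intervention will be conducted within one primary healthcare organization".
- **The enrolment answer.** Section 5.1.1 defines the primary outcome as "assessed at enrolment and after one month by a one item question", so a baseline value of the outcome exists for each patient.

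On timing, section 3 has the intervention begin when the patient is identified as needing palliative care. Section 5.2 describes team training first and then says "Secondly, the research team will perform an assessment of baseline measurements in participating patients". Section 7.2 keeps enrolment open during the study. On recruitment, section 5.2 has teams told their allocation, section 7.2 has the team's own nurses screen and approach patients, and section 5.2 says "The intervention group will be educated in identifying patients with PC needs".

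**The concern.** The analysis should normally reflect the randomisation. A stratum left out of the model leaves between-organisation variation in the team-level error, although stratification has removed it from the comparison. The standard error is then too large.

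The enrolment answer is a harder case, because two risks pull in opposite directions. Teams are randomised, not patients. Patients are recruited after allocation by nurses who know it, and only one arm is trained to identify them. If the arms enrol different patients, a model without the enrolment answer attributes part of that difference to the intervention. But if the answer is given after care under the intervention has begun, it is partly an outcome, and adjusting for it takes away real effect. The documents do not say which situation applies.

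The design has little reserve. Section 4.4 sizes the trial at the smallest ICC in its table and states no allowance for dropout.

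**Working it through.** **Inputs from section 4.4:** 30% against 40%, 20 patients per team, 20 teams per arm (400 patients), alpha 5% (taken as two-sided), ICC 0.001 to 0.02. The organisation difference, the correlation r between the enrolment and one-month answers, and any enrolment imbalance are not in the documents. They are assumed over ranges.

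**1. Reproduce the plan.** Variance = 2 × 0.35 × 0.65 × DE / 400, with DE = 1 + 19 × ICC and a noncentral t with 38 df. With df = 2(k − 1) for k teams per arm, the method returns all eight rows of Table 1 (26/23/21/20 and 5/4/4/4). At ICC 0.001, DE = 1.019, SE = 0.0340 and noncentrality = 0.10 / 0.0340 = 2.94. Power with 20 teams per arm is 81.7/78.9/75.5/69.1% at ICC 0.001/0.005/0.01/0.02.

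**2. Organisation: ceiling at the planned ICC.** Two equal organisations that differ by d contribute (d/2)² / (0.35 × 0.65) to the ICC. This is 0.0010, 0.0027 and 0.0110 for 3, 5 and 10 points. If 0.001 is the total ICC, d cannot exceed about 3 points. The most the term can then do is move ICC 0.001 on 38 df to ICC 0 on 37 df: 81.66% to 82.31%, about 0.7 points.

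**3. Organisation: larger differences.** Simulation of 40 teams (20 per organisation), within-organisation ICC 0.001, team-level linear model as an approximation to the mixed logistic model:

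| Difference | Allocation | Type I error without term | Power without / with term |
|---|---|---|---|
| 5 points | 10 per arm per organisation | 4.4% | about 80.5 / 82% |
| 10 points | 10 per arm per organisation | about 3% | about 76 / 82% |
| 5 points | coin toss | 4.9–5.1% | 78.9 / 79.9% |
| 10 points | coin toss | 4.9–5.1% | 73.1 / 80.3% |
| none | coin toss | 4.9–5.1% | 80.7 / 79.6% |

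A random-intercept logistic simulation (balanced allocation, 700 runs per setting) agrees. With control rates of 25% and 35%, type I error without the term is 4.0% and power goes from 77% to 82% when it is added. The odds ratio is unchanged.

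**4. Enrolment answer, taken before the intervention, arms comparable.** The variance is multiplied by (1 − r²). At r = 0.2/0.3/0.4/0.5, power is about 83/85/88/91% at ICC 0.001 and 71/73/77/81% at ICC 0.02. If the four listed covariates already carry half of this information, the gain at r = 0.3 is only 1.7 to 2.1 points.

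**5. Enrolment answer, taken before the intervention, arms not comparable, no true effect.** With 30% in both arms, SE = √(2 × 0.30 × 0.70 × 1.019 / 400) = 0.0327. An imbalance of b points at enrolment carries over as r × b.

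- b = 5, r = 0.3: 1.5 points, noncentrality 0.46, rejection 7.3%.
- b = 10, r = 0.3: 3.0 points, noncentrality 0.92, rejection 14.5%.

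The logistic simulation (25% yes at enrolment against 30–35%; prognostic odds ratio 3 or 6) gives a spurious odds ratio of 1.06–1.20 and type I error of 6.6–19.1% without the answer. With it, the odds ratio is about 1.00 and type I error 3.6–4.6%.

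**6. Enrolment answer already moved by the intervention.** An early shift of s points cancels the whole gain when (10 − r·s)/√(1 − r²) = 10, so s = 10 × (1 − √(1 − r²))/r. This is 1.0/1.5/2.1/2.7 points at r = 0.2/0.3/0.4/0.5. A 3-point shift leaves 78.4/78.0/78.5/80.2% power at ICC 0.001, all below 81.7%. In the logistic simulation a 5- to 10-point shift lowers the odds ratio from 1.56 to 1.42–1.51 and power from 82–84% to 57–73% (three of four planned settings completed).

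**7. Which odds ratio.** The marginal value is (0.4/0.6)/(0.3/0.7) = 1.56. Conditional on the enrolment answer (30% yes assumed), the same effect is about 1.59/1.63/1.69/1.80 at r = 0.2/0.3/0.4/0.5.

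**The case against.** The plan has a fair defence.

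- At the planned ICC the organisation term is worth less than a point of power. The larger gains need an organisation difference that no document gives. This stands, and limits the size of the point. The term costs little, however, and follows the randomisation.
- Every correlation and imbalance is assumed, and performance status and diagnosis may already carry much of what the enrolment answer would add. This also stands; step 4 shows the smaller gain.
- Leaving the enrolment answer out is defensible while its timing is open. Agreed: the request is to settle the timing, not simply to add the variable.
- The data management plan (section 6) lists a separate analysis plan that was not supplied, and its own overview is only an abstract. The fuller plan may hold more. The two supplied texts nevertheless agree on the same four covariates.

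A reader might infer that both omissions cost precision only. For the enrolment answer the documents do not support that: randomising teams does not balance patients whom unblinded nurses recruit afterwards. A reader might also infer the opposite, that the trial will be biased. Nothing in the documents shows that an imbalance will occur, or in which direction.

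Section 3's reference to randomising inside one organisation, set against the two organisations in sections 4.1 and 5.2, may look like a contradiction. It can mean within each organisation, which is what stratification does, so it is loose wording. The remark in section 2.4 of the data management plan that data are gathered after implementation answers a question about data reuse and is not relied on for timing.

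**Conclusion.** Both omissions are real, and they differ in kind. Omitting organisation is a matter of power only: no bias, no inflated type I error, and a conservative test if arms are balanced within organisation. The cost runs from at most about 0.7 points at a total ICC of 0.001 to about 6 points at an assumed 10-point difference with balanced allocation.

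Omitting the enrolment answer is harmless apart from precision only if the arms enrol comparable patients. An assumed 5- or 10-point imbalance at correlation 0.3 would give type I error of about 7% or 15%. Including it is safe only if it is recorded before care under the intervention. Sections 3 and 5.2 suggest that it may not be, but they do not settle the matter. If it is not, adjustment removes part of the effect, and a shift of 1 to 3 points already cancels the gain.

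This is an improvement to consider, not a fatal flaw. Confidence is medium, because the sizes rest on assumed organisation differences, correlations and imbalances.

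**What to change.** In section 6.1, and in the Plan Overview where the model is repeated:

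1. Specify a random intercept for nursing team and fixed effects for allocation, homecare organisation and the four listed covariates. State whether team numbers are balanced within organisation, and clarify the wording in section 3. Cost: one degree of freedom, and at most about 1 point of power if the organisations are alike and arms are assigned by coin toss.
2. State when the enrolment answer is taken relative to care under the intervention, reconciling sections 3, 5.2 and 7.2, and report the answer by arm.
3. Include it in the primary model only if it is recorded before that care. Otherwise use it only in a sensitivity analysis, noting that adjustment then cannot separate selection from effect. Cost: with training described first and enrolment continuing, early recording has to be built into the enrolment procedure and may not be feasible.
4. Because adding the answer changes the conditional odds ratio, state in advance which odds ratio is reported and give a marginal risk difference beside it.

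The separate analysis plan should carry the same model.
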